2.5. Exploratory Objectives / Endpoints

- To collect and store plasma, serum and archival tumour samples or paired tumour biopsies and analyse surplus blood or tissue, if available, for potential future exploratory research into factors that may influence development of cancer and/or response to AZD4547 (where response is defined broadly to include efficacy, tolerability or safety)
- To investigate PK/PD relationships including serum FGF23, serum phosphate levels, serum FGF-2 (safety run-in only)
- To analyse a range of oncology biomarkers, which may correlate with drug response
- To investigate the association between FGFR1 FISH score and the above primary and secondary efficacy endpoints (safety run-in only)

3. STUDY DESIGN

This study protocol has undergone peer review as part of the process of endorsement by the Cancer Research UK New Agents Committee

3.1. Overall Study Design

This is a phase IIa (with safety run-in), multi-centre, open label, single arm study of AZD4547 administered orally together with anastrozole or letrozole in ER+ breast cancer patients who have progressed on treatment with anastrozole or letrozole; in adjuvant or first line metastatic (safety run-in only) or any setting (phase IIa only). There are two parts to this study: an initial safety run-in followed by a phase IIa study.

Safety run-in: Two safety run-ins will be conducted to assess the safety and tolerability of AZD4547 in combination with anastrozole and in combination with letrozole. Between 3 and 12 patients will be enrolled into each of the safety run-in parts of the study (i.e. 6 to 24 in total). In both parts, the first cohort will receive 80 mg bd AZD4547. The total number of patients will depend upon the number of cohorts necessary (see Figure 1). A cohort will have a minimum of 3 and maximum of 6 patients (see

Figure 2). The Safety Review Committee (SRC) will determine the dose de-escalation scheme, whether further cohorts are required, and ultimately select the safe and tolerated dose of AZD4547 to be used in the phase IIa study. A different dose level of AZD4547 may be selected for combination with anastrozole than for letrozole.

Phase IIa: 50 patients will be recruited to receive study treatment (see Figure 3).

3.2. Treatment Regimens

Safety run-in:

Initially, patients will continue to receive the single agent treatment which they have progressed on: either anastrozole (1mg) or letrozole (2.5mg), orally, once daily for 7 days. N.B. this must be preceded by a minimum of 21 days of anastrozole or letrozole treatment prior to study entry.

Oral AZD4547 will then be added to this ongoing non-steroidal aromatase inhibitor therapy twice daily but on an intermittent schedule of one week on/one week off.

Phase IIa:

[figure not shown]
Patients will continue or restart the NSAI which they have progressed* on: either anastrozole (1mg) or letrozole (2.5mg), orally, once daily but together with twice daily AZD4547 (80mg); the confirmed dose level for AZD4547 determined during the safety run-in part of the study.

*Prior to study entry, patients must have taken anastrozole or letrozole at some stage in their treatment to date for breast cancer; and shown evidence of resistance to this therapy. The NSAI does not have to be the most recent line of treatment.

AZD4547 will be given on an intermittent schedule of one week on / one week off. This schedule has been well tolerated in the preceding safety run-in part of the study. However, if 2 or more cases of severe toxicity (leading to permanent discontinuation of study drug) are observed in the first 6 patients, the Independent Data Monitoring Committee (IDMC) will consider an alternative schedule of two weeks on / one week off, if emerging data from other AZD4547 studies suggest that this is a better tolerated schedule.

3.3. Study Flow Charts

Figure 1: Study Flow Chart – Safety run-in for both Anastrozole and Letrozole

¹anastrozole or letrozole

Figure 2: Safety run-in - Dosing Algorithm Within a Cohort

[figure not shown]
[figure not shown]

Figure 3: Study flow chart Phase IIa

3.4. Follow-up

All patients on AZD4547 and either anastrozole or letrozole should be followed for 28 days after the last dose of study treatment for complete safety data.

3.5. Study Termination

The study will be terminated when:

- All patients on AZD4547 and either anastrozole or letrozole combination therapy have permanently discontinued study medication due to progression or unacceptable toxicity, and completed 28 days follow-up for collection of safety data

3.5.1. Treatment after Study Termination

Following participation in the study, patient care will be decided by their local doctor according to usual practice.

4. PATIENT SELECTION AND RECRUITMENT

4.1. Screening and Enrolment

Each patient will undergo screening during the 28 days prior to admission to confirm eligibility. Tumour assessments and other clinical data obtained as standard of care prior to consent may be used for the study provided they comply with the protocol specified timelines. Written informed consent will be obtained before the subject undergoes any study specific procedures.

Each potential patient will be assigned a unique identifier number for use during the trial. A complete record of all patients who enter screening for the study, and also those who go on to be enrolled, must be maintained at each site. The local investigator is responsible for ensuring that this record includes the allocated trial ID as well as the patient identifiable data including name, hospital number and date of birth.

Eligible patients who take part in the study must meet all of the listed inclusion criteria and none of the exclusion criteria. NB. Some criteria are relevant for the safety run-in or phase IIa parts of the study only; these are marked accordingly.

4.2. Subject Selection

4.2.1. Inclusion Criteria

Patients must fulfil all of the following criteria.

1. Written (signed and dated) informed consent and be capable of co-operating with treatment and follow-up
2. Aged ≥ 25 years of age (N.B. in line with other studies with AZD4574 and due to concerns of possible effects on the immature skeleton)
3. Post menopausal women. Women will be considered postmenopausal if they have had a bilateral oophorectomy or the following specific requirements apply:

Safety run-in:

- Women under 50 years old would be considered post-menopausal if they have been amenorrhoeic for 24 months and have follicle-stimulating hormone (FSH) and oestradiol levels in the post-menopausal range. Patients with prior exposure to depot LHRH analogues must be 24 months or more following the last administration
- Women aged 50 years and older would be considered post-menopausal if they have been amenorrhoeic for 12 months and patients with prior exposure to depot LHRH analogues must be 12 months or more following the last administration
- Women rendered amenorrhoeic by adjuvant chemotherapy, who were premenopausal or perimenopausal prior to chemotherapy, must have been amenorrhoeic for at least 24 months

Phase IIa:

- Women under 50 years old would be considered post-menopausal if they have been amenorrhoeic for 24 months and have follicle-stimulating hormone (FSH) and oestradiol levels in the post-menopausal range.
- Women aged 50 years and older would be considered post-menopausal if they have been amenorrhoeic for 12 months
- Women rendered amenorrhoeic by adjuvant chemotherapy, who were premenopausal or perimenopausal prior to chemotherapy, must have been amenorrhoeic for at least 24 months
- Perimenopausal women rendered amenorrhoeic from exposure to depot LHRH analogues*

*Patients must have taken LHRH analogues for at least 6 months

4. Eastern Cooperative Oncology Group (ECOG) performance status 0-1 with no deterioration over the previous 2 weeks and minimum life expectancy of 12 weeks
5. Histological confirmation of breast cancer with documented positive oestrogen receptor status (ER+) of primary or metastatic tumour tissue according to local laboratory parameters
6. **Phase IIa:** Mandatory provision of tumour biopsy for assessment of oncology biomarkers
7. Fulfils criteria for previous treatment of breast cancer*:

Safety run-in:

- Relapse during a single regimen of adjuvant endocrine therapy with either anastrozole or letrozole
or
- Progression during first line endocrine therapy with a non-steroidal AI for advanced breast cancer**. Co-administration of a targeted agent with the non-steroidal AI is permitted providing all toxicities have recovered to CTCAE Grade 1 or below

1 prior regimen of chemotherapy in the advanced setting is permitted. Chemotherapy administered in the adjuvant setting is permitted

Phase IIa:

- Progressing or progression at some point during breast cancer treatment on endocrine therapy with a non-steroidal AI.*** Co-administration of a targeted agent with the non-steroidal AI is permitted providing all toxicities have recovered to CTCAE Grade 1 or below.
- Prior chemotherapy in the advanced and adjuvant setting is permitted.
- Prior treatment with exemestane with or without everolimus is permitted.

*HER2-positive breast cancer patients should have been offered at least one prior line of HER2 directed therapy

**Advanced breast cancer: metastatic disease or locally advanced disease which is not amenable to treatment with curative intent

***anastrozole or letrozole does not have to be the most recent therapy

8. **Safety run-in:** At least one lesion (measurable and/or non-measurable) that can be accurately assessed by CT/MRI/plain x-ray at baseline and follow up visits

Phase IIa: At least one lesion $\geq 10\text{mm}$ in the longest diameter at baseline (or $\geq 15\text{mm}$ in the short axis for nodal disease) that can be accurately measured with CT/MRI at baseline and is suitable for accurate repeated measurements. Patients with bone only metastatic cancer must have a lytic or mixed lytic-blastic lesion that can be accurately assessed by CT or MRI.

9. **Safety run-in:** Study entry must be preceded by a minimum of 21 days of anastrozole or letrozole treatment

Phase IIa: No set duration of anastrozole or letrozole treatment prior to study entry.

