No reproductive toxicology or teratogenic studies have been conducted with AZD4547 to date, and it is unknown whether the drug is excreted in human milk. This study is being conducted in postmenopausal women only and so this is not considered a relevant risk in this study.

Possible Drug Interactions

AZD4547 is a substrate of CYP3A4 and CYP2D6 therefore use of inhibitors/inducers of these isoforms will be excluded from 2 weeks prior to the first dose of AZD4547 and for the duration of study treatment. CYP1A1, an isoform highly inducible by cigarette smoking, is also capable of metabolism of AZD4547 and may lead to lower exposures in smokers, therefore smoking status will be recorded as part of the demographic information for all participating patients. AZD4547 shows weak competitive inhibition of CYP3A4 and is also a time-dependent inhibitor of this isoform. This may lead to reduced metabolism (and increased exposure) of any co-administered drugs that are significantly cleared via this pathway. Concomitant use of medicines significantly metabolised by CYP3A4 will be contraindicated during the course of the study. Use of other agents less significantly metabolised will be permitted with caution if considered clinically indicated for the welfare of the patients, and patients will be closely monitored for possible drug interactions.

Overall Benefit-Risk Assessment

In the advanced cancer setting that has been chosen for this study, prolonged survival rates are very low and there is a large unmet clinical need for novel therapeutic agents.

Although there can be no certainty of clinical benefit to patients, non-clinical data with AZD4547 support the hypothesis that FGFR inhibition may be a valid target for the treatment of tumours driven via this pathway. The non-clinical safety profile has not identified any risks that would preclude

investigation in this setting, and monitoring is in place for those risks deemed to be most likely or serious.

Investigation of AZD4547 in this patient population is justified, based upon the non-clinical safety profile, the limited life expectancy due to malignant disease, and the strength of the scientific hypothesis under evaluation. Thus the benefit/risk assessment for this study supports the oral administration of AZD4547 together with anastrozole or letrozole to patients with advanced cancer, according to the proposed study design.

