6.2.11. Drug Interactions/Precautions

6.2.11.1. Restrictions

The following restrictions apply while the patient is receiving study treatment and for the specified times before and after:

1. All patients should avoid concomitant use of drugs, herbal supplements and/or ingestion of foods known to modulate CYP3A4 or CYP2D6 enzyme activity and drugs that are known to be CYP3A4 substrates from the time they enter the screening period until 2 weeks after the last dose of study treatment. Please refer to Appendix B for further details.
2. Patients must not use oestrogen-containing agents such as hormone replacement therapy.
3. Patients with uncontrolled glaucoma or intra-ocular pressure ≥ 21 mm Hg at screening should be referred for ophthalmological management and the condition controlled prior to first dose.

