6.2.11.2. Concomitant Treatments

Information on any treatment in the 4 weeks prior to starting study treatment and all concomitant treatments given during the study, with reasons for the treatment, will be recorded in the CRF. If medically feasible, patients taking regular medication, with the exception of potent inhibitors or inducers of CYP3A4 or CYP2D6 or substrates of CYP3A4, should be maintained on it throughout the study period.

Patients should not be administered calcium-containing phosphate chelation agents, such as calcium acetate, for the management of hyperphosphataemia whilst receiving study treatment due to the increased risk of precipitating ectopic tissue mineralisation.

Other anticancer agents, investigational agents and radiotherapy should not be given while the patient is on study treatment although radiation for palliation at focal sites is permitted.

Patients may receive treatment with corticosteroids and/or bisphosphonates for the treatment of bone metastases.

Patients may take warfarin or a coumarin preparation but it is recommended that they should have their anticoagulation monitored carefully and dose adjusted accordingly.

Supportive care and other medications that are considered necessary for the patient's well-being may be given at the discretion of the Investigator.

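### Section 1.6.4 sets aside an unstudied reproductive risk because all patients are postmenopausal, but Phase IIa admits perimenopausal women with LHRH-induced amenorrhoea and gives them no reproductive safeguard

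*Protocol*

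**What the plan says.** Protocol section 1.6.4, under Reproductive Organs, states that "No reproductive toxicology or teratogenic studies have been conducted with AZD4547 to date". It then disposes of the risk in one sentence: "This study is being conducted in postmenopausal women only and so this is not considered a relevant risk in this study". It offers no other mitigation.

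Section 4.2.1, criterion 3, defines who counts as postmenopausal, with separate lists for the two parts of the study. The Phase IIa list includes "Perimenopausal women rendered amenorrhoeic from exposure to depot LHRH analogues", with the footnote "Patients must have taken LHRH analogues for at least 6 months". No other condition attaches to that route.

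Two provisions in section 6.2.11 bear on what these women may take during the study. Section 6.2.11.1 says "Patients must not use oestrogen-containing agents such as hormone replacement therapy". Section 6.2.11.2 says of patients on regular medication that, if medically feasible, they "should be maintained on it throughout the study period". The same section also bars other anticancer agents during study treatment; the only exception in that sentence is focal palliative radiotherapy.

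**The concern.** The waiver in 1.6.4 rests on a biological fact: no participant can become pregnant. Criterion 3 classes the LHRH group as postmenopausal for eligibility, but its own wording calls these women perimenopausal and attributes their amenorrhoea to a drug. A classification for entry does not supply the fact that the waiver needs.

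A site following the protocol as written could give AZD4547 to a woman whose ovarian suppression is drug-induced and may lapse. She would have no pregnancy test, no contraception advice required by the protocol, and no procedure if she became pregnant. A site could also read 6.2.11.2 as requiring her to stop the drug that made her eligible.

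**Working it through.** No arithmetic applies. The check compares the stated entry conditions, then looks for a safeguard elsewhere in the protocol.

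**Step 1: entry conditions in criterion 3 of section 4.2.1**

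| Part | Group | Minimum amenorrhoea | Condition on LHRH analogue | FSH and oestradiol check |
|---|---|---|---|---|
| Safety run-in | Under 50 | 24 months | At least 24 months since last dose, if exposed | Yes |
| Safety run-in | 50 and over | 12 months | At least 12 months since last dose, if exposed | No |
| Phase IIa | Under 50, standard route | 24 months | None | Yes |
| Phase IIa | 50 and over, standard route | 12 months | None | No |
| Phase IIa | Chemotherapy-induced | 24 months | None | No |
| Phase IIa | LHRH-induced, perimenopausal | None stated | At least 6 months of use | No |

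**Step 2: does the protocol itself treat induced amenorrhoea as possibly reversible?** It does, in two places.

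- In the run-in, for women aged 50 and over, "patients with prior exposure to depot LHRH analogues must be 12 months or more following the last administration"; for women under 50 the interval is 24 months.
- The Phase IIa list retains this rule: "Women rendered amenorrhoeic by adjuvant chemotherapy, who were premenopausal or perimenopausal prior to chemotherapy, must have been amenorrhoeic for at least 24 months".

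Both rules make sense only if amenorrhoea brought on by treatment may not be permanent. The LHRH route has no counterpart to either.

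**Step 3: must the analogue be current or continue?** The footnote asks that it has been taken for at least 6 months, which past use satisfies. The instruction in 6.2.11.2 to maintain regular medication is conditional and does not name LHRH analogues. The bar on other anticancer agents in the same section has no LHRH exception. Whether the analogue must continue, or even may, is therefore not settled.

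**Step 4: is there a safeguard elsewhere?**

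- Exclusion criteria (4.2.2): no mention of pregnancy or lactation.
- Study plan (Table 2) and laboratory evaluations (5.2.17): chemistry, haematology and dipstick urinalysis for glucose, protein and blood; no pregnancy test.
- Restrictions (6.2.11.1): no contraception rule.
- Reasons for discontinuation (6.3.1): pregnancy is not listed.
- Pharmacovigilance (section 7): no pregnancy notification or follow-up. The only related text is the standard birth-defect criterion for a serious adverse event in 7.6, which captures one late outcome.

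**Step 5: who could enter by this route?** The minimum age is 25 and the route sets no age limit of its own. The protocol does not say how many such women are expected.

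**The case against.** The strongest reply has five parts.

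1. *The text is formally consistent.* Criterion 3 says such women will be considered postmenopausal, so 1.6.4 is true under the protocol's own definition. That is correct as wording, but it does not make the stated reason apply to women described in the same line as perimenopausal.

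2. *The comparisons are not like for like.* The run-in rule tests for natural menopause after the drug has worn off, whereas the Phase IIa route accepts suppression maintained by the drug, so a washout would defeat its purpose. Nor is a postmenopausal hormone range the right test for that route. This stands: neither a washout nor an FSH check is the remedy. The earlier rules still show that the protocol regards induced amenorrhoea as possibly reversible.

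3. *The natural reading is ongoing use.* The eligibility line suggests established treatment, regular medication should be maintained, Appendix B does not list LHRH analogues, and the investigator may give other medication needed for well-being. A site would have to admit a woman because of her analogue and then stop it. That is unlikely, but nothing in the text excludes it, and nothing excludes a woman whose use ended before entry.

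4. *Safeguards may sit elsewhere.* The pharmacovigilance manual cited in 7.7 and the consent documents are not available for this review and could cover pregnancy reporting or contraception. This stands as a limit on those two absences. It cannot repair 1.6.4 or criterion 3, and the missing test in Table 2 is plain.

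5. *Pregnancy is improbable in this population.* Perhaps so, but the protocol does not argue this. Its single argument is menopausal status.

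**Conclusion.** The concern holds. Section 1.6.4 gives one reason for setting aside an unstudied hazard, and that reason is untrue for a group that Phase IIa expressly admits. The entry condition for that group is 6 months of analogue use, with no stated requirement of current use, continuation or minimum amenorrhoea. Comparable induced amenorrhoea after chemotherapy requires 24 months.

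The size of the risk cannot be stated because the number of women entering by this route is not given; it could be none. The conclusion assumes that the protocol text shown is complete on screening tests, restrictions and eligibility. It makes no claim about the consent documents or the pharmacovigilance manual. There is no effect on sample size, error rates or the primary endpoint. It should be fixed because it is a wrong safety premise, not merely missing detail.

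**What to change.** 1. **Section 1.6.4:** state that Phase IIa may include women whose ovarian function is suppressed by an LHRH analogue, and that reproductive risk is relevant to them.
2. **Section 4.2.1, criterion 3 (Phase IIa):** require women entering by this route to be on an LHRH analogue at entry, after at least 6 months of use, and to continue it throughout AZD4547 treatment.
3. **Section 6.2.11.2:** name the LHRH analogue as an exception to the bar on other anticancer agents.
4. **For this subgroup only:** add a screening pregnancy test to Table 2, a contraception rule to 6.2.11.1 and a pregnancy-reporting procedure to section 7. Contraception must be oestrogen-free, since 6.2.11.1 already bars oestrogen-containing agents.

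Items 1 to 3 close most of the gap; item 4 covers a lapse in suppression.

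The cost is amendment wording in these sections and one simple screening test for a subgroup of unknown size. No woman who stays on her analogue is lost. A woman who has stopped it would have to qualify by another route. The sample size and analysis are unchanged.

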4.2.2. Exclusion Criteria

1. Treatment with any of the following:
 - a. **Safety run-in:** more than 1 regimen of endocrine therapy for advanced breast cancer
 - b. previous exposure to any FGFR inhibitor
 - c. **Safety run in:** more than 1 prior regimen of chemotherapy for advanced breast cancer.
 - d. potent inhibitors or inducers of CYP3A4 or CYP2D6, or substrates of CYP3A4 within 2 weeks prior to first dose of study treatment (3 weeks for St John's Wort)
 - e. major surgery within 4 weeks prior to first dose of study treatment
 - f. radiotherapy with a wide field of radiation within 4 weeks prior to first dose of study treatment; or radiotherapy with a limited field of radiation for palliation within 2 weeks before the first dose of study treatment
2. With the exception of alopecia, any unresolved toxicities from prior therapy greater than CTCAE grade 1 at time of starting study
3. Spinal cord compression or brain metastases unless asymptomatic, treated and stable and not requiring steroids for at least 4 weeks prior to start of study treatment
4. Any evidence of severe or uncontrolled systemic diseases or active infection
5. Any of the following cardiac criteria:
 - a. Resting corrected QT interval (QTc) >470 ms
 - b. Any clinically important abnormalities in rhythm, conduction or morphology of resting ECG e.g. complete left bundle branch block, third degree heart block
 - c. Any factors that increase the risk of QTc prolongation or risk of arrhythmic events such as heart failure, hypokalaemia, congenital long QT syndrome, family history of long QT syndrome or unexplained sudden death under 40 years of age or any concomitant medication known to prolong the QT interval
6. Inadequate bone marrow reserve or organ function as defined by any one of the following parameters:

Haemoglobin < 9.0 g/dL (<90.0 g/L)
Absolute neutrophil count (ANC) < 1.5×10^9 /L
Platelet count < 100×10^9 /L
Alanine aminotransferase > 2.5 x ULN if no demonstrable liver metastases or > 5 x ULN in the presence of liver metastases
Aspartate aminotransferase > 2.5 x ULN if no demonstrable liver metastases or > 5 x ULN in the presence of liver metastases
Total bilirubin > 1.5 x ULN if no demonstrable liver metastases or > 3 x ULN in the presence of liver metastases
Creatinine > 1.5 times ULN or creatinine clearance <50ml/min
Corrected calcium > ULN
Phosphate > ULN
7. Refractory nausea and vomiting, chronic gastrointestinal diseases, inability to swallow the formulated IMP or previous significant bowel resection that would preclude absorption of AZD4547 or anastrozole or letrozole
8. History of hypersensitivity to anastrozole or letrozole
9. History of another malignancy within 5 yrs prior to starting study treatment, except adequately treated basal or squamous cell carcinoma of the skin, carcinoma of the cervix and the disease under study

10. Any of the following ophthalmological criteria:*

- Current evidence or previous history of retinal pigmented epithelium detachment (RPED)
- Previous laser treatment or intra-ocular injection for treatment of macular degeneration
- Current evidence or previous history of soft drusen, drusenoid RPE detachment and wet macular degeneration.
- Current evidence or previous history of retinal vein occlusion (RVO)
- Current evidence or previous history of retinal degenerative diseases (e.g. hereditary)

*Patients with uncontrolled glaucoma or intra-ocular pressure >21 mmHg at screening should be referred for ophthalmological management and the condition controlled prior to first dose of study treatment.

11. Concurrent treatment with another investigational agent or use of another investigational agent within 30 days or 5 half lives, whichever is longer, preceding the first dose of study treatment
12. Concurrent treatment with prohibited medications and wash out period for that drug will not have been completed before starting study medication (see Appendix B)

